## 1. PROTOCOL SUMMARY

Title	Assessment of Wound Closure Comparing Synthetic Hybrid-Scale Fiber Matrix with Standard of Care in Treating Diabetic Foot Ulcer
Protocol Number	21-RES-002; Revision: 002
Protocol Approval Date	07NOV2022
Study Sponsor	Acera Surgical, Inc.
Indications for Use	Restrata® is intended for use in the management of wounds, including: Partial and full thickness wounds, pressure sores / ulcers, venous ulcers, diabetic ulcers, chronic vascular ulcers, tunneled / undermined wounds, surgical wounds (e.g., donor site / grafts, postlaser surgery, post-Mohs surgery, podiatric wounds, dehisced wounds), trauma wounds (e.g., abrasions, lacerations, partial thickness burns, skin tears), draining wounds.
Study Product	Synthetic Hybrid-Scale Fiber Matrix (Restrata®)
Study Purpose	Comparatively assess wound closure in diabetic foot ulcers treated with synthetic hybrid-scale fiber matrix or standard of care in a randomized clinical trial.
Enrollment Size	48 subjects (24 subjects in the experimental arm and 24 subjects in the control arm)
Study Design	Prospective, randomized, controlled, single-blind clinical trial
Primary Outcome Measure	

Diabetic Foot Ulcers: Complete re-epithelialization of wounds within 12 weeks after the initial application of the study product plus confirmation of no drainage or need for additional dressing 2 weeks after complete re-epithelialization

Secondary Outcome Measure	

Decrease in wound area

Time from initial application of study product to complete re-epithelialization of wound

Total number of product applications

Tertiary Outcome Measure	

Quality of Life - SF-36 Questionnaire

Incidence of adverse events

Cost effectiveness / economic model (amount of product usage, length of treatment)

Assessment Timepoints	

Run-In Period to verify enrollment criteria: 2 weeks before initial application of study product

Product Application: Weekly application (or as needed based on the clinician discretion and ongoing wound assessment) for either 12 weeks or until complete reepithelialization (whichever occurs first)

	

➤ Wound assessment, measurement, and AEs: Day of initial product application and weekly for either 12 weeks or until complete re-epithelialization (whichever occurs first)

➤ Quality of Life and Pain Assessments: Day of initial product application and at either complete reepithelialization or 12 weeks (whichever occurs first)

➤ For patients with complete re-epithelialization:

○ Clinic visit two weeks after complete re-epithelialization to verify wound closure, drainage, and need for additional dressing

--	---

## 2. INTRODUCTION & PURPOSE

### 2.1. Background and Purpose

Diabetes and peripheral vascular disease are both growing healthcare problems that can lead to chronic wounds by compromising skin integrity and impairing the wound healing process. Chronic wounds affect more than 6.5 million patients annually in the United States. In particular, many diabetic foot ulcers (DFUs) fail to heal with standard options such as debridement, dressings, and infection control. Skin substitutes can regenerate tissue and replace lost skin for wounds that are otherwise difficult to treat.

The process of wound healing requires a coordinated effort of cellular recruitment and tissue growth. Regenerative matrix materials have been used as a skin substitute to promote this coordination and provide immediate wound coverage to minimize the risks associated with infection and fluid loss. An ideal material for these purposes would serve as a healing scaffold, limit infection risk, minimize inflammation, be readily available for use, and be conformable to diverse wound surfaces.

To support the infiltration of fibroblasts, the deposition of new collagen, and reepithelialization of the wound surface, the wound matrix material should persist in the wound for several weeks. The timing of wound matrix degradation is therefore critical, as the wound matrix should resist degradation until sufficient new tissue growth has occurred. The susceptibility of biologic wound matrix materials to enzymatic degradation leads to a resorption rate that is poorly controlled, risking the premature degradation of the wound matrix prior to sufficient wound healing.

There remains a need for materials that minimize inflammation and promote complete wound healing. Electrospun fibrous scaffolds may meet this need by

mimicking the structure of native extracellular environment while enabling resident cells to perform their roles in the healing cascade.

In 2018, a retrospective study was completed to evaluate clinical efficacy and utility of Restrata, a synthetic skin substitute. The study examined 82 chronic wounds including 34 DFUs, 34 VLUs, and 14 other chronic wounds (pressure ulcers, traumatic and postsurgical wounds, nonvenous vascular wounds and necrotic wounds). Synthetic hybrid-scale fiber matrix was applied weekly, or as deemed appropriate for up to 12 weeks. Overall, treated wounds demonstrated progressive and sustained wound area reduction over the course of treatment, with 85 percent achieving complete closure at 12 weeks.

Based on these clinical findings a prospective, non-randomized, single-arm, single-blind study was conducted at 5 centers across the United States as a pilot for an expanded randomized controlled trial. In the study wounds were prepared using standard methods or debridement, and synthetic hybrid-scale fiber matrix was then applied to the wound so that it completely contacted the entire surface of the wound bed. A non-adherent primary wound dressing was then applied, followed by appropriate secondary dressing to manage the wound exudate and moisture. Post-application, wounds were examined weekly for signs of infection, wound progression, and tissue healing for up to 12 weeks, or until complete closure, which was confirmed 2 weeks thereafter. The wound area was measured, wound appearance was photographed, and wound closure was documented if present. Synthetic hybrid-scale fiber matrix was then re-applied weekly or as deemed appropriate.

At the end of the 12-week treatment period, complete wound closure occurred in 75.0% (18/24) of patients who received synthetic hybrid-scale fiber matrix. The average wound area reduction over 12 weeks was 96%, and the average time to complete wound closure was 6.4 weeks. A significant increase in epithelialization was observed from the initial to the final assessment ( $p<0.0001$ , Wilcoxon matched-pairs signed rank test), with nearly complete covering seen at final assessment. This was paralleled by a significant decrease in the amount of wound exudate ( $p<0.0001$ ) to a nearly dry wound at the final assessment, and complete disappearance of necrotic tissue over time ( $p=0.0001$ ). An average of 4.3 scaffolds were used per patient over the treatment period. Fixation was used to hold all scaffolds in place, with the most popular fixation technique being the use of Steri-Strips. The decision of the frequency of re-application was solely at the discretion of the clinician who was treating the wounds, and results found that half of the patients received reapplication of the nanofiber matrix on a weekly basis, whereas the other half of the patients had less frequent re-application rates. Neither fixation technique nor application frequency were found to have a statistically significant effect on

complete wound closure ( $p=0.41$ , Chi-square test and  $p=0.64$ , Fisher's exact test, respectively). In total, the clinical results suggest that synthetic hybrid-scale fiber matrix offers a new and unique alternative in the treatment of chronic DFUs and assists in properly powering an expanded multi-center randomized controlled clinical trial.

## **2.2. Purpose**

The purpose of the following prospective, randomized, controlled clinical trial is to compare synthetic hybrid-scale fiber matrix (Restrata®, Acera Surgical, Inc.) with standard of care in treating diabetic foot ulcers in human subjects.

This study is being conducted to provide information on healing success with a new category of synthetic skin substitutes recently created by the Centers for Medicare and Medicaid Services (CMS). The study will demonstrate utilization of synthetic hybrid-scale fiber matrix in generating wound healing outcomes; including time to wound epithelialization, decrease in wound size, and total number of study product applications prior to healing. This data is valuable to the payor community with coverage decisions.

## **2.3. Intended Use/Indications**

Restrata® is a sterile, single use device intended for use in local management of wounds. Restrata® is a soft, white, conformable, non-friable, absorbable matrix that provides a moist environment for the body's natural healing process to occur. Restrata® is made from synthetic biocompatible materials and was designed to include a fibrous structure with high porosity, similar to native extracellular matrix. Restrata® is a porous matrix with a defined rate of resorption that provides a scaffold for cellular infiltration and vascularization before completely degrading via hydrolysis. The device permits the ingress of cells and soft tissue formation in the defect space / wound bed. The device does not contain any human or animal materials or tissues.

Restrata® is terminally sterilized, in a single use double peel package in a variety of sizes. Contents of the package are guaranteed sterile and non-pyrogenic unless the package has been opened or damaged.

Restrata® is intended for use in the management of wounds, including: Partial and full thickness wounds, pressure sores / ulcers, venous ulcers, diabetic ulcers, chronic vascular ulcers, tunneled / undermined wounds, surgical wounds (e.g., donor site / grafts, postlaser surgery, post-Mohs surgery, podiatric wounds, dehisced wounds), trauma wounds (e.g., abrasions, lacerations, partial thickness burns, skin tears), draining wounds. Utilization of Restrata® in the treatment of diabetic foot ulcers,

as proposed in the present study, is therefore considered “on label” and is not considered experimental.

The benefits and risks of participation in this study will be described in the informed consent form.

## **2.4. Standard of Care**

The standard of care for established chronic wounds incorporates common principles, including:

- Removing necrotic tissue through debridement.
- Maintaining moisture balance by selecting the proper wound dressing to control exudate.
- Taking measures to prevent or treat wound infections.
- Correcting ischemia in the wound area.
- Applying offloading device in the case of diabetic foot ulcers)

Subjects randomized to the Standard of Care (control) arm will have their wounds debrided weekly. An appropriate dressing (foam or alginate dressing) will then be applied to maintain wound moisture balance in the wound, and changed daily. An appropriate offloading device (CAM boots or surgical shoes) will also be utilized depending on the wound location, condition and patient’s health status.

## **3. STUDY DESIGN**

**Condition:** Diabetic Foot Ulcer (DFU)

**Aim:** Comparatively assess wound closure in diabetic foot ulcers treated with synthetic hybrid-scale fiber matrix or standard of care in a randomized, controlled clinical trial.

**Number of Patients:** 48 subjects (24 subjects in the experimental arm and 24 subjects in the control arm)

**Number of Sites:** 2

**Study Type:** Interventional

**Study Design:** Allocation: Randomized (1:1 ratio)  
Endpoint Classification: Efficacy  
Intervention Model: Direct assignment

Masking: Single Blind (Subject)

Primary Purpose: Treatment

**Control Group:** Treatment with Standard of Care (weekly)

**Test Group:** Treatment with Synthetic Hybrid-Scale Fiber Matrix (weekly or as needed based on the clinician discretion and ongoing wound assessment)

#### **Primary Outcome Measures:**

- Complete re-epithelialization of wound as assessed by the evaluator within 12 weeks after the initial application of the study product plus confirmation of no drainage or need for additional dressing 2 weeks after complete re-epithelialization.

#### **Secondary Outcome Measures:**

- Decrease in Wound Area From Initial Application  
Wound area measurements will be made via acetate tracing every week for 12 weeks or until complete reepithelialization, whichever occurs first.
- Time to Complete Re-epithelialization  
The number of weeks from initial application of study product until complete reepithelialization is first identified.
- Number of Product Applications  
The number of study product applications including the initial application until 12 weeks for DFU patients or until complete reepithelialization, whichever occurs first.

#### **Tertiary Outcome Measures:**

- Quality of Life (SF-36)  
Day of initial application and at either 12 weeks or at complete re-epithelialization (whichever occurs first).

- Incidence of adverse events
- Cost effectiveness / Economic model (amount of product usage, length of treatment)

The following information will be provided for each subject:

- CPT Codes
- HCPCS Codes
- ICD-10 codes
- DRGs (if applicable)
- Dates of Service/Range of service
- Place of Service
- Bill type (131, etc.)

## 4. PATIENT SELECTION

### 4.1. Inclusion Criteria

1. Patient is at least 18 years old
2. Patient is willing and capable of complying with all protocol requirements
3. Patient or legally authorized representative (LAR) is willing to provide written informed consent prior to or at the beginning of the run-in period
4. Patient has Type 1 or Type 2 diabetes (criteria for the diagnosis of diabetes mellitus per American Diabetes Association)
5. Ulcer must be located at least in part on the foot or ankle
6. Ulcer must be present for a minimum of 28 days prior to randomization and initial application of study product
7. Wound size must be  $\leq 30 \text{ cm}^2$  on the day of randomization and initial application of the study product, after initial debridement
8. Patient has adequate circulation to the affected extremity, as demonstrated by at least ONE of the following within 60 days prior to enrollment/randomization:
  - a. Dorsum transcutaneous oxygen test (TcPO2) of study leg with results  $\geq 40 \text{ mmHg}$ , OR
  - b. Ankle-Brachial Index (ABI) of study leg with results of  $\geq 0.7$  OR

- c. Toe-Brachial Index (TBI) of study extremity with results of > 50 mmHg

#### **4.2. Exclusion Criteria**

1. Patient has been previously enrolled into this study, or is currently participating in another drug or device study that has not reached its primary endpoint
2. Patient is pregnant, breast feeding or planning to become pregnant
3. Patient has a known allergy to resorbable suture materials, e.g. Polyglactin 910 (PGLA), Polydioxanone (PDS)
4. Patient has a life expectancy less than six months as assessed by the investigator
5. Patient has received skin substitutes during the run-in period or within 14 days prior to beginning of run-in period
6. Patient has an additional wound within 3 cm of the study wound
7. Hgb A1c > 12% within 3 months prior to randomization in patients with a known history of diabetes
8. Patient not in reasonable metabolic control in the judgment of the investigator
9. Patient with a known history of poor compliance with medical treatments
10. Patient currently undergoing cancer treatment
11. Patient has been diagnosed with at least one of the following autoimmune connective tissue diseases: lupus, vasculitis, sickle cell, or uncontrolled rheumatoid arthritis
12. Patient is taking parenteral corticosteroids or any cytotoxic agents for 7 consecutive days during the run-in period or up to 30 days before the run-in period. Chronic oral steroid use is not excluded if dose is < 10 mg per day for prednisone.
13. Active infection, undrained abscess, or critical colonization of the wound with bacteria in the judgment of the investigator
14. Osteomyelitis or exposed bone, probes to bone or joint capsule on investigator's exam or radiographic evidence
15. Patient unwilling to or unable to safely utilize appropriate offloading device to unweight wound

16. Study ulcer experiences spontaneous closure over the 2-week run in period

## 5. STUDY CONDUCT

### 5.1. Schedule of Events

The schedule of events for this study is outlined in Appendix A.

### 5.2. Screening

A patient screening log will be maintained. For patients who do not meet eligibility criteria, the reason(s) for exclusion from the study will be documented.

Patients will undergo the benefit insurance verification process via the third-party Reimbursement Support Hotline prior to or during the run-in period. Product Reimbursement will be confirmed for the synthetic hybrid-scale fiber matrix and related services and procedures incurred during the study period.

### 5.3. Informed consent

Prior to the start of the 2-week run-in period and the completion of any non-standard of care study activities, written informed consent shall be obtained from the patient or the patient's legally authorized representative (LAR). The investigator (or designee) must ensure that each patient (or LAR) is fully informed about the nature of the study, study objectives, study products, study procedures, and possible risks and benefits associated with participation in this study. Information shall be provided to the patient (or LAR) in a language and level of complexity so that he/she understands. The patient (or LAR) will have adequate time to consider participation in the study and have the opportunity to ask questions. The patient (or LAR) will sign and date the informed consent form, and he/she shall be provided a signed copy of the form. The investigator (or designee) will retain each patient's original signed informed consent form.

If significant new information is obtained after a patient is enrolled, the patient will be informed about the new information if the patient has not exited the study. Any discussions with the patient about new information should be documented. Patients will sign a new informed consent form at the discretion of the investigator and/or the IRB/EC.

The initial informed consent form and any revisions made during the course of the study must be approved by both the IRB/EC and Acera Surgical, Inc. before use.

## 5.4. Run-in Period

A 2-week run-in period will be required prior to enrollment/randomization and treatment in order to complete screening assessments and confirm that the wound has spontaneously closed. Written informed consent must be obtained prior to or at the beginning of the run-in period.

### 5.4.1. First Visit of Run-In Period (14 to 17 days before randomization)

An in-person visit will be completed at the beginning of the 2-week run-in period, and the following will be completed:

- Written informed consent will be obtained
- Assessment of inclusion/exclusion criteria
- Collection of demographics and medical history information
- Assessment of HbA1c in patients with known history of diabetes if it was not completed within the previous 73 days
- If vascularization in the study leg was not assessed within the previous 42 days, then at least ONE of the following shall be completed:
  - Ankle-brachial index (ABI) of study leg
  - Toe-brachial index (TBI) of study extremity
  - TcPO2 of study leg
- Assessment of ulcer size
- Assessment of wound for signs of infection, wound progression, and tissue healing. Gross observation will be utilized to determine the need for change in dressing type or dressing replacement/change.

**NOTE: Informed consent must be obtained prior to the above assessments if they are not considered standard of care at this visit.**

If the patient does not continue to meet all inclusion/exclusion criteria by the end of the visit, then they will be considered a screen failure and should not proceed with additional visits/assessments.

#### **5.4.2. Second Visit of Run-In Period (7 days $\pm$ 3 days After First Visit)**

An in-person visit will be completed 7 days after the first run-in visit ( $\pm$  3 days), and the following will be completed:

- Assessment of ulcer size
- Assessment of wound through gross observation and analysis for signs of infection, wound progression, and tissue healing. Gross observation will be utilized to determine the necessity of standard dressing change.
- Continued assessment of inclusion/exclusion criteria.

If the patient does not continue to meet all inclusion/exclusion criteria, then they will be considered a screen failure and should not proceed with additional visits/assessments.

### **5.5. Point of Enrollment**

Patients will be considered enrolled after ALL of the following requirements are met:

- Written informed consent is provided
- The patient meets all inclusion criteria
- The patient meets no exclusion criteria
- The patient has completed the 2-week run-in period without spontaneous closure
- The patient is randomized

### **5.6. Randomization**

The randomization process will be finalized prior to enrollment of the first study patient. Once the patient meets all enrollment criteria and has completed the 2-week run-in period, the patient will be randomized. Patients will be randomized to receive either synthetic hybrid-scale fiber matrix (treatment group) or standard of care treatment (control group). Appendix B presents the randomization plan.

Randomization will be stratified by wound size:

Patients will fall into two groups ( $< 12.5 \text{ cm}^2$ ) and ( $\geq 12.5 \text{ cm}^2$  and  $\leq 30 \text{ cm}^2$ ). Patients within each group will be randomized in a 1:1 ratio to receive either synthetic hybrid-scale fiber matrix or standard of care treatment.

Once the patient is ready to be randomized, the randomization form will be completed by study personnel. Any patients that exit the study before randomization

are considered screen failures. A study exit CRF shall be completed if the patient is not eligible for randomization.

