### **7.3. Sample Size Calculation**

Sample size calculations were performed using a Farrington & Manning test for superiority of the synthetic hybrid-scale fiber matrix group compared to the control group. Under assumptions of a closure rate of 80% for the synthetic hybrid-scale fiber matrix group, 40% for the control group, and a superiority margin of 10%, this results in a sample size of 20 per group (40 total) that provides a power of 0.8 and one-sided alpha of 0.05. After allowing for an assumed 20% lost to follow up, this results in a total sample size of 48 patients.

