### **7.4. Interim and Final Analyses**

An unblinded interim assessment for sample size re-estimation (SSR) will be performed on the primary endpoint of the study by an independent statistician. The analysis will be conducted when 50% of the mITT population (24 patients) have been enrolled and completed the primary endpoint evaluation. The analysis described below will be performed on the mITT population.

The purposes of the interim analysis are (1) to calculate the power for superiority, conditioned on the interim-observed difference between treatments with respect to 100% re-epithelialization rates and on the superiority margin of 10%, and (2) determine if the sample size needs to be increased in order to maintain the desired conditional power of 80%.

The conditional power will be calculated under the assumption that the interim observed estimate of the treatment difference is the true treatment difference. It will be calculated using the following formula as discussed in Lan and Wittes (1988) where:

$$1 - \Phi\left[\frac{Z_{1-\alpha} - B_\tau / \tau}{\sqrt{1-\tau}}\right]$$

$Z_{1-\alpha}$  is the  $(1-\alpha) \times 100\%$  percentile of the standard normal distribution (i.e., the critical value used to assess superiority at the final analysis at overall one-sided significance level  $\alpha$ ).

$\tau$  is the information fraction (= proportion of patients in the first interim analysis =  $r/M$  where  $r$  is the number of patients per group in the interim analysis and  $M$  is the planned number of patients per group for the final analysis); if the interim sample sizes per group are not equal due to randomness, the harmonic mean of the sample size will be used.

$B_\tau = Z_\tau \sqrt{\tau}$  where  $Z_\tau$  = the Farrington-Manning non-inferiority test statistic calculated on the interim observed data.  $\Phi$  is the cumulative distribution function of the standard normal distribution.

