## **7.6. Study Outcome**

### **7.6.1. Primary Endpoints**

100% re-epithelialization will be assessed every week for 12 weeks or until 100% re-epithelialization, whichever occurs first. Persistence of wound closure will be verified via confirmatory visit within 2 weeks after complete closure has been first determined.

For the primary endpoint of 100% re-epithelialization at week 12 a two-stage analysis will test first if the rate of 100% re-epithelialization is superior between groups using a chi squared and/or Farrington & Manning test. Superiority for synthetic hybrid-scale fiber matrix will be demonstrated if the lower bound of the 90% CI of the difference in proportions lies above the superiority margin of +10%.

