## Appendix B: Randomization Plan

# A Randomization Plan for patients with wound size < 12.5 cm^2

from

<http://www.randomization.com>

1. Standard of Care \_\_\_\_\_
2. Restrata \_\_\_\_\_
3. Restrata \_\_\_\_\_
4. Standard of Care \_\_\_\_\_
5. Restrata \_\_\_\_\_
6. Standard of Care \_\_\_\_\_
7. Restrata \_\_\_\_\_
8. Standard of Care \_\_\_\_\_
9. Restrata \_\_\_\_\_
10. Standard of Care \_\_\_\_\_
11. Restrata \_\_\_\_\_
12. Standard of Care \_\_\_\_\_
13. Standard of Care \_\_\_\_\_
14. Restrata \_\_\_\_\_
15. Restrata \_\_\_\_\_
16. Restrata \_\_\_\_\_
17. Restrata \_\_\_\_\_
18. Standard of Care \_\_\_\_\_
19. Standard of Care \_\_\_\_\_
20. Restrata \_\_\_\_\_
21. Standard of Care \_\_\_\_\_
22. Restrata \_\_\_\_\_
23. Standard of Care \_\_\_\_\_
24. Standard of Care \_\_\_\_\_

24 subjects randomized into 2 blocks

To reproduce this plan, use the seed 24156

along with the number of subjects per block/number of blocks  
and (case-sensitive) treatment labels as entered originally.

Randomization plan created on 3/26/2021, 1:14:54 PM

**A Randomization Plan for patients with wound size  
of  $\geq 12.5 \text{ cm}^2$  and  $\leq 30 \text{ cm}^2$**   
from  

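### Randomisation is stratified by wound size but no described test uses the strata; the unstratified test is approximately valid and gives up power only if wound size predicts closure strongly and in the same direction in both arms

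*Combined protocol and SAP*

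**What the plan says.** Section 5.6: "Randomization will be stratified by wound size", in two groups (below 12.5 cm², and 12.5 to 30 cm²), and "Patients within each group will be randomized in a 1:1 ratio". Appendix B has a separate list of 24 places for each group, 12 per arm, each noted as "24 subjects randomized into 2 blocks".

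The tests are described without these groups:

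- **Primary analysis (7.6.1).** The closure rate is tested as "superior between groups using a chi squared and/or Farrington & Manning test". Success requires that "the lower bound of the 90% CI of the difference in proportions lies above the superiority margin of +10" per cent.
- **Interim (7.4).** Z_τ is "the Farrington-Manning non-inferiority test statistic calculated on the interim observed data". Unequal arm sizes are provided for ("if the interim sample sizes per group are not equal due to randomness, the harmonic mean of the sample size will be used"), but strata are not.
- **Missing data (7.8).** A one-sided Farrington-Manning test is run on each of 50 imputed datasets. The imputation model names age and gender and leaves further variables to a formal statistical analysis plan.

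No reason is given for leaving the strata out. Section 7.3 sizes the trial thus: "Under assumptions of a closure rate of 80% for the synthetic hybrid-scale fiber matrix group, 40% for the control group", with a margin of 10% and one-sided alpha of 0.05.

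**The concern.** Stratified allocation forces balance on wound size. If wound size predicts closure, that balance makes the true sampling variance of the difference smaller than the unstratified formula assumes. The interval is then wider than it needs to be, and the benefit of stratifying is not collected in the analysis. One bound against +10% decides the trial, so in borderline data the choice of test can decide the result. The documents do not settle that choice: 7.6.1 leaves the test open between two methods, and 7.4 sends unblinded interim results to a sponsor group.

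**Working it through.** **1. The plan's own figure.** From the inputs in 7.3, the unpooled formula gives n = (1.645 + 0.842)² × (0.8×0.2 + 0.4×0.6) / (0.40 − 0.10)² = 6.18 × 0.40 / 0.09 = 27.5, so 28 per group. The Farrington-Manning calculation gives 31. The stated 20 does not reproduce. Exact unstratified power is 65.0% at 20 per arm and 72.9% at 24. That shortfall is a separate point; here it is only the baseline.

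**2. Effect of stratified allocation on the variance.** Assume equal strata. The gap is the small-wound minus the large-wound closure rate, g_T in the device arm and g_C in controls. The unstratified per-patient variance is 0.16 + 0.24 = 0.40. The true one is 0.40 − (g_T² + g_C²)/4. With g_C = 0.3:

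- same gap in the device arm: 0.40 − 0.045 = 0.355, a cut of 11%;
- half the gap: 0.40 − 0.028 = 0.372, a cut of 7%;
- flat device rate: 0.40 − 0.0225 = 0.3775, a cut of 6%.

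Normal approximation at 24 per arm, same gap 0.3:

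- unstratified: (0.30 − 1.645×√(0.40/24)) / √(0.355/24) = 0.72, power 76.4%;
- stratified: 0.30/√(0.355/24) − 1.645 = 0.82, power 79.4%.

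A stratified score test does not always recover the whole cut, because it estimates each stratum's variance under a difference of exactly +0.10. It works best when the gap runs the same way in both arms. With opposite gaps of 0.3, simulated power is 74.1% unstratified and 72.2% stratified.

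**3. Exact enumeration.** Unstratified Farrington-Manning against a stratified score test: strata weighted by size, restricted variance in each stratum times N/(N−1), 80% vs 40%, margin 0.10, one-sided 0.05. Entries are power differences in points, stratified minus unstratified.

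| Pattern | Per arm | Gap 0 | 0.1 | 0.2 | 0.3 | 0.4 |
|---|---|---|---|---|---|---|
| Same gap | 24 | -1.8 | -1.0 | +0.8 | +2.9 | +5.9 |
| Same gap | 20 | -2.7 | -2.0 | +0.3 | +3.9 | +8.3 |
| Half gap, device | 24 | -1.8 | -1.4 | -0.4 | +1.0 | +2.5 |
| Half gap, device | 20 | -2.7 | -2.3 | -1.1 | +0.9 | +3.5 |
| Flat, device | 24 | -1.8 | -1.6 | -1.3 | -0.7 | 0.0 |
| Flat, device | 20 | -2.7 | -2.6 | -2.1 | -1.3 | -0.2 |

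Break-even gaps are about 0.17 to 0.19 (same), 0.24 to 0.27 (half) and 0.40 to 0.46 (flat). A gap of 0.4 in both arms implies device rates of 100% and 60%, an extreme case.

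**4. Source of the loss at small gaps.** It is the N/(N−1) factor, not the stratification. At gap 0 and 24 per arm, power is 72.9% unstratified, 71.1% stratified with the factor and 73.9% without it. Without the factor, however, size at 50% vs 40% is about 5.4 to 5.9% over gaps 0 to 0.4 (same or half gap).

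**5. Size, 24 per arm, same gap, gaps 0 to 0.4.**

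- 50% vs 40%: unstratified 5.1, 5.0, 4.7, 4.2, 3.6%; stratified with the factor 4.6, 4.7, 5.0, 5.3, 5.2%.
- 70% vs 60%: unstratified 5.6, 5.5, 5.2, 4.7, 4.0%; stratified with the factor 5.0 to 5.3%.

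**6. A borderline result.** Take 18/24 (the pilot rate in 2.1) against 10/24. Unstratified: p = 0.0494, lower bound 0.101. Stratified, with closures 11+7 vs 8+2 (small + large wounds): p = 0.0353, bound 0.122.

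**7. Interim.** On the Appendix B lists, 24 patients split 12+12 by stratum give 6 device and 6 control in each. Split 16+8, the smaller stratum has 4 and 4; split 18+6, it has 3 and 3. With an unstratified Z_τ and a stratified final test, overall size was 4.3 to 5.1% in simulation, at 50% vs 40% only and with the cap of 70 read as a total.

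**8. Imputation.** Assume gap 0.3 (device rates 95% and 65%), device-arm dropout of 10% in small and 30% in large wounds, and age and gender unrelated to wound size. Imputing by arm without wound size gives (0.9×0.95 + 0.7×0.65)/1.6 = 0.819, an overstatement of 1.9 points. The same pattern in controls gives (0.9×0.55 + 0.7×0.25)/1.6 = 0.419, also +1.9, so the difference is unbiased. The reverse pattern in controls gives 0.381, and the difference is then overstated by about 3.8 points.

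**The case against.** The strongest reply is that this is a preference between two acceptable tests. Nothing in the documents shows that wound size predicts closure. At 24 per arm and gaps up to 0.3 the power change runs only from -1.8 to +2.9 points over the three patterns in the table, and the two tests reach different verdicts in 2.5 to 3.3% of trials (3.1 to 5.5% at 20 per arm). The formal analysis plan mentioned in 7.8 may also define the test. All of this stands, and it makes the point an improvement to consider and not an error. It does not remove the case for fixing the choice in writing before unblinded data exist.

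A reader might infer more than the documents support:

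- **That ignoring the strata makes the test invalid.** It does not. With the same gap in both arms the size falls as the gap grows.
- **That the present test is always on the safe side at large gaps.** This holds only for the same gap in both arms. At 70% vs 60%, 20 per arm and gap 0.3, unstratified size is 5.2 to 5.3% with a half gap or a flat device rate, a small excess due to discreteness.
- **That any prognostic effect costs power.** At a common gap of 0.1 the proposed test is the weaker one.
- **That 18/24 vs 10/24 shows stratification overturning a success when closures are even across strata.** Stratified p is then 0.0531, but only through the N/(N−1) factor; without it p is 0.0494, as for the unstratified test.
- **That the imputation model is already biased.** Under the dropout assumptions above the bias cancels when pattern and gap are the same in both arms, and 7.8 leaves the further variables open.

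**Conclusion.** The point holds in a limited form. Allocation is stratified, the described tests are not, and no reason is given. The unstratified test is approximately valid. A stratified test would gain about 3 to 4 points of power at a common gap of 0.3 (24 and 20 per arm) and 6 to 8 at the extreme gap of 0.4. It would lose about 1 to 3 points if wound size is weakly prognostic or matters only in controls. These figures assume 80% vs 40%, equal strata, complete data and no sample size increase. Every gap is assumed, so confidence that there is a net gain is moderate. The case for prespecifying the choice is firmer, because the choice can decide a borderline result. The simulation of overall size supports an unstratified Z_τ only for one null rate and one reading of the cap: 7.4 defines M' per group, so 70 per group is also possible, and Appendix B stops at 48 places in total.

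**What to change.** Before the unblinded interim:

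- **7.6.1.** Make primary the wound-size-stratified Farrington-Manning/Miettinen-Nurminen score test at +0.10: strata as randomised, weights by stratum size, the N/(N−1) factor stated explicitly, one-sided 0.05. Its matching 90% interval must have a lower bound above +0.10. Keep the unstratified test as a sensitivity analysis.
- **7.8.** Run the same test on each imputed dataset and name wound-size stratum among the imputation variables. This guards against bias where dropout by wound size differs between arms.
- **7.4.** State that Z_τ stays unstratified because interim cells within a stratum can be as small as 3 or 4 per arm. Repeat the check of overall size at other null rates and with 70 per group.
- **Formal analysis plan.** If the test is defined there, make the same changes there.

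The cost is wording in three sections, some reprogramming and a further simulation. No new data are needed, since stratum is known at randomisation. The downside is the 1 to 3 points of power given above. The change does not repair the shortfall against the stated 80% power: at 20 per arm and gaps up to 0.3 either test gives about 62 to 70%.
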